## 7.10 Survival Follow-up

Each patient will be followed for survival every 3 months ( $\pm$  14 days) after patient's final protocol treatment with DEC-C or venetoclax (whichever occurs last) until death, end of the study, until patient withdraws consent, or for a maximum of 2 years after the patient's final protocol-indicated treatment – whichever comes first. Survival contact can be made via clinic visit, chart review, obituary or similar observation (e.g. Social Security death index), or by telephone.

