11. During the first three days of therapy, tumor lysis syndrome (TLS) precautions will include scheduled outpatient visits with TLS laboratory studies. Therapy with a uric acid reducing agent (e.g., allopurinol initiated at least 2-3 days prior to the start of therapy) is required. Laboratory monitoring for TLS (per institution standard of care) will occur prior to the first dose on cycle 1 day 1 and continue for the first three days of cycle 1. Unless contraindicated, allopurinol must be continued through the end of cycle 1. Intravenous fluids should be administered daily during the ramp-up period. Patients with clinical evidence of TLS should be hospitalized.
12. The study will provide decitabine/cedazuridine (DEC-C) to the sites. Treatment with DEC-C will begin on Cycle 1 Day 1 after receiving anti-TLS hydration/prophylaxis. It is intended that patients will receive DEC-C until progression of disease, unacceptable toxicity, revocation of consent, or for up to 12 months of post-remission therapy. DEC-C is to be taken without food at the same time each day. See [Section 5.2.1.2](#).
13. Sites will obtain commercial (standard of care) venetoclax. Venetoclax will begin on Cycle 1 Day 1 after receiving anti-TLS hydration/prophylaxis. Venetoclax dosing is ramped to 400mg/day. It is intended that patients will receive venetoclax until progression of disease, unacceptable toxicity, revocation of consent, or for up to 12 months of maintenance. Venetoclax is taken with food at the same time each day. See [Section 5.2.1.1](#).
14. On Cycle 1, Day 1 only: Physical exam; ECOG performance status; and weight will be obtained unless performed within the prior 7 days. Confirmation of a negative pregnancy test is required in all women of childbearing potential prior to beginning protocol-directed therapies.
15. All patients will undergo bone marrow aspiration and biopsy on cycle 1 day 22 to assess treatment response and for correlative studies. Patients with at least a partial response (PR) to treatment who receive a second cycle of full-intensity therapy will have repeat biopsy at cycle 2 day 22. Aspirate and matching PD blood samples will be sent for correlative studies.

16. Beginning in the post-remission phase: To accommodate scheduling, Day 1 and 15 visits/procedures may occur with flexibility of  $\pm$  3 days.

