### **2.2 Secondary Objectives:**

1. To assess the rate of partial response (PR) and morphologic leukemia free state (MLFS) following treatment with DEC-C/venetoclax
2. To assess the relapse free survival of patients treated with DEC-C/venetoclax
3. To assess overall survival of patients treated with DEC-C/venetoclax
4. To assess the safety and tolerability of DEC-C/venetoclax in the post-HCT setting
5. To assess the rates of measurable residual disease negativity in patients achieving a CR.

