### 3.2 Study Duration and Dates

It is estimated that this study will enroll patients from January 2022 through January 2024. Data lock and study closure is expected in January 2025.

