### 9.3.1 General Analysis Considerations

Continuous variables (e.g., age) will be summarized using the minimum, 25th, 50th (median), 75th, and maximum values along with the mean and standard deviation, as appropriate. Generally, rank based nonparametric tests will be used to compare continuous variables among patient subgroups. Categorical variables (e.g., objective response) will be summarized in frequency tables and compared among patient subgroups using the chi-square test. Linear regression and logistic (or ordinal logistic) regression will be used to construct multivariable models for continuous, binary, and ordinal variables, as appropriate. In addition to ORR, the distributions of progression-free and overall survival will be estimated using the Kaplan-Meier method. We will consider statistical comparisons statistically, but not necessarily clinically, significant for  $p<0.05$ .

Dose limiting toxicity (see [Section 5.2.4](#)) will be monitored in this phase II clinical trial using a Bayesian approach. A maximum of 34 patients will be enrolled and toxicity monitoring will begin when the 6th patient is evaluable for toxicity. It is expected that the toxicity rate is maintained at approximately 20% (maximum probability of DLT of 0.2, prior distribution (1,1), cohort size 1, and posterior probability  $> 80\%$ ). Pursuant to this rule, patients will be monitored according to the stopping boundaries outlined in [Table 10](#). For example, the protocol will pause for review due to excessive toxicity if 2 or more DLTs are experienced by the first 6 patients treated. 9 DLTs will be allowed among 34 patients treated.

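### Survival follow-up is capped at 2 years after the last dose, so overall-survival censoring after about 24 months depends on how long the patient was treated

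*Combined protocol and SAP*

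**What the plan says.** Overall survival is a secondary objective in section 2.2: "To assess overall survival of patients treated with DEC-C/venetoclax". Section 9.3.1 gives the method: "the distributions of progression-free and overall survival will be estimated using the Kaplan-Meier method". It states no time origin and no censoring rule for overall survival.

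Section 7.10, repeated in Note 20, has survival contacts every 3 months "until death, end of the study, until patient withdraws consent", or "for a maximum of 2 years after the patient's final protocol-indicated treatment", whichever is earliest. The 2-year limit is counted from the last dose of either drug, not from Cycle 1 Day 1 (C1D1).

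The last-dose date varies widely. Note 12 continues treatment until progression, unacceptable toxicity or withdrawal of consent, "or for up to 12 months of post-remission therapy". With one or two pre-remission cycles before that, a responder may be treated for about 13 to 14 months, or longer if count recovery delays cycles. A non-responder may stop after one or two cycles.

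Section 3.2 gives the calendar, as an estimate: "this study will enroll patients from January 2022 through January 2024", and "Data lock and study closure is expected in January 2025".

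**The concern.** Kaplan-Meier assumes that a patient censored at a given time has the same outlook as those still at risk then. A cap counted from last dose makes the longest possible follow-up equal to treatment duration plus 24 months. Treatment duration reflects response and tolerance, both of which may bear on survival. In effect, the method credits each capped patient with the later mortality of those left in the risk set, who are more often patients treated for longer.

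At stake is the tail of the overall-survival curve. The background section cites a registry analysis with 3-year survival below 5% for relapse within 6 months of transplant and 12% for relapse at 6 to 24 months. A reader may set the trial's tail beside those figures, although the plan specifies no such comparison.

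**Working it through.** The plan gives no survival rate, event count or precision for overall survival, so there is no stated figure to reproduce.

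**When the cap binds.** Let A be months from January 2022 to C1D1 and D months from C1D1 to last dose. Measured from C1D1, closure in January 2025 falls at 36 − A and the cap at 24 + D. The cap comes first when 24 + D < 36 − A, that is, when A + D < 12.

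- D = 1: binds if A < 11.
- D = 2: binds if A < 10.
- D = 6: binds if A < 6.
- D = 12 or more: never binds before closure.

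Two patients enrolled in January 2022 show the contrast. One treated for 1.5 months and still alive is censored at 25.5 months. One treated for 12 months can be followed to 36. Because the cap is never earlier than 24 months from C1D1, it cannot affect the curve up to that point.

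**Size and direction.** This needs assumptions that the documents do not supply: exponential survival by response group; non-responders treated 1.5 months; responders' treatment time exponential with median 6 months, truncated at 14; uniform accrual over 24 months; closure at month 36. Each scenario used 400,000 simulated patients. Entries are true overall survival, then the Kaplan-Meier value under the cap; errors are differences of the rounded values.

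| Scenario (response rate; median survival in non-responders / responders, months) | 30 months | 35.5 months | Error at 35.5 months |
|---|---|---|---|
| A: 35%; 4 / 12 | 6.6%, 6.8% | 4.7%, 5.0% | +0.3 |
| B: 35%; 6 / 18 | 13.1%, 13.8% | 10.0%, 11.1% | +1.1 |
| C: 15%; 4 / 12 | 3.1%, 3.5% | 2.1%, 2.4% | +0.3 |
| F: 35%; 8 / 24 | 19.5%, 20.9% | 15.5%, 18.0% | +2.5 |
| D: as A, with 10% long-term survivors in both groups | 13.3%, 12.8% | 11.2%, 10.2% | −1.0 |
| E: as A, with 10% long-term survivors among non-responders only | 11.3%, 10.6% | 9.2%, 7.8% | −1.4 |

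Long-term survivors have a hazard of 0.01 per month. In every scenario the 24-month value is correct to within 0.1 point, and dropping the cap brings the later values to within 0.1 point of truth.

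**How many patients.** Scaled to N = 34, the cap censors 0.4 (C) to 2.3 (F) patients alive; varying the assumptions further gives up to about 2.5. The expected number at risk at 30 months without the cap is 34 × S(30) × 6/24, since only the first 6 of 24 accrual months allow 30 months of follow-up:

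- A: 34 × 0.066 × 0.25 = 0.56, against 0.26 with the cap.
- F: 34 × 0.195 × 0.25 = 1.66, against 0.62 with the cap.

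The cap removes more than half of a very small risk set.

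**Sampling error.** Even with complete follow-up of 34 patients, the standard error in scenario B at 35.5 months would be √(0.100 × 0.900 / 34) = 5.1 points. With the actual censoring, the standard deviation of the 35-month estimate is about 7 to 10 points in simulated 34-patient trials with responder / non-responder medians of 18 / 4 and 24 / 8 months.

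**If closure slips.** The dates are estimates. With no calendar closure, the cap censors 1.2 to 7.4 of 34 patients alive. The error at 36 months is −1.5 to +2.4 points, and the curve ends at about 24 + 14 = 38 months.

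**The case against.** A reader might infer that the rule biases the survival curve upward. The documents do not support that. Everyone censored by the cap has already survived 2 years off treatment. An exponential model gives surviving non-responders their original high hazard, which forces an upward error; scenarios D and E reverse it. With medians 18 / 4 and 10% long-term survivors among early stoppers, 35-month survival is 13.8% true against 13.0% capped. With medians 24 / 8 and the same 10%, the error stays upward (20.2% against 21.4%). The sign is unknown before the data are seen.

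A reader might also infer that the cap is what leaves mainly responders in the tail. Most of that has happened before the cap acts. With medians 18 / 4 and 35% response, responders alive at 24 months are 0.35 × 2^(−24/18) = 0.139 of all patients and non-responders 0.65 × 2^(−24/4) = 0.010, so responders are already 93% of survivors (68% with medians 24 / 8). Nor is early stopping the same as non-response: a responder who stops for toxicity at 3 months is capped at 27 months, close to a non-responder's 25 to 26.

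The remaining objections concern size, and they stand. Study closure, which does not depend on treatment, is the main limit after 24 months. Few patients are at risk there with or without the cap. Overall survival is descriptive, with no planned test against the registry figures, and a useful 3-year estimate is out of reach under this calendar anyway. None of this removes the dependence of censoring on treatment duration; it makes the point a minor one.

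**Conclusion.** The point holds as a small defect that is cheap to remove. For patients enrolled in about the first year, maximum survival follow-up depends on treatment duration, and hence on response or toxicity, so overall survival after about 24 months from C1D1 is open to informative censoring of unknown sign. In the scenarios examined the 35.5-month error lies between about −1.4 and +2.5 points, well inside sampling error. These sizes rest on the assumed survival and treatment-time distributions and on the planned dates; the dependence itself follows from sections 3.2 and 7.10 alone. Overall survival to 24 months and the composite complete remission rate are unaffected.

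**What to change.** In section 7.10 and Note 20, remove the limit counted from last dose. Follow every patient for survival to death, consent withdrawal or the common data lock, using the chart-review, telephone and death-index routes that 7.10 already allows. In section 9.3.1, state the time origin (for example C1D1) and the censoring rule for overall survival.

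If the cap is kept, say in 9.3.1 that the overall-survival curve is estimated and plotted only to 24 months from C1D1, with numbers at risk shown.

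While editing, reconcile 7.10 with section 5.2.13, which sits under an off-treatment heading but speaks of taking participants off the study at progression; survival follow-up should clearly continue after that.

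The cost is a few extra survival checks, for roughly 0.4 to 2.5 expected patients under the planned calendar and more if closure is delayed, plus two or three sentences of text. Sample size, the primary analysis and treatment rules do not change.

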17. Reasonable effort should be made to complete End-of-Treatment (EOT) procedures on the day it is decided a patient will no longer receive protocol-indicated treatment. These procedures must be completed subsequent to and not later than 10 days after investigator decision to permanently discontinue protocol-indicated treatment with DEC-C or venetoclax (whichever treatment occurs last) and prior to any subsequent anti-cancer therapy.
18. At End-of-Treatment: If patient discontinues study treatment for reason other than progressive disease confirmed by biopsy procedure (e.g. due to adverse event), then every effort should be made to obtain fresh biopsy samples to evaluate response and to obtain biospecimens including matching PD blood samples for exploratory research. If progressive disease is suspected between scheduled study biopsies (e.g. due to peripheral blood counts), then fresh biopsy and PD blood samples must be collected in a subsequent procedure to evaluate for progressive disease and to obtain bio specimens for research purposes; if progressive disease is confirmed in that procedure and the patient will terminate the study as a result, then these procedures may be used as the end of treatment procedures.
19. Follow-up clinic visit to be completed within 28 to 35 days after patient's final protocol-indicated treatment with DEC-C or venetoclax (whichever occurs last). Documented attempt(s) must be made for patient return to the study clinic. It will not be considered a protocol deviation if the patient is physically unable to return for the follow-up visit; such circumstance should be recorded in the study documents, and as much of the follow-up information as possible should be obtained from local and outside facilities. Note: The study may continue to request results of laboratory data conducted outside of the study but related to peripheral blood counts or bone marrow biopsy, until progressive disease is ultimately confirmed.
20. Each patient will be followed for survival every 3 months ( $\pm$  14 days) after patient's final protocol treatment with DEC-C or venetoclax (whichever occurs last) until death, end of the study, until patient withdraws consent, or for a maximum of 2 years after the patient's final protocol-indicated treatment – whichever comes first. Survival contact can be made via clinic visit, chart review, obituary or similar observation (e.g. Social Security death index), or by telephone.

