## 7.9 28 Day Follow-up Visit Assessments

Documented attempt(s) must be made for patient return to the study clinic. It will not be considered a protocol deviation if the patient is physically unable to return for the follow-up visit; such circumstance should be recorded in the study documents, and as much of the follow-up information as possible should be obtained via feasible patient contact and from local and outside facilities.

A Follow-up clinic visit is to be completed 28 days (+7 days) after patient's final protocol-indicated treatment venetoclax or DEC-C (whichever occurs last), in order to undergo the following assessments:

- Physical Exam
- ECOG performance status
- Weight
- Vital signs: Blood pressure (BP), heart rate (HR) and temperature.
- Concomitant medication and adverse event review.
- CBC with differential
- Blood chemistry

For patients who discontinue study treatment for reason other than progressive disease confirmed by bone marrow aspiration and biopsy (e.g. suspicious peripheral blood counts), please note the study may continue to request results of laboratory data conducted outside of the study but related to peripheral blood counts or bone marrow examination, until progressive disease following venetoclax/DEC-C is ultimately confirmed by marrow procedure.

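### After the 28-day visit, relapse data are optional and later therapy is not collected, so relapse-free survival may be overstated or cut short, depending on a censoring rule the plan does not give

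*Combined protocol and SAP*

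**What the plan says.** Section 2.2 lists as a secondary objective: "To assess the relapse free survival of patients treated with DEC-C/venetoclax". Section 9.3.1 does not name RFS. It says that "the distributions of progression-free and overall survival will be estimated using the Kaplan-Meier method", and no section defines RFS events, time origin or censoring.

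Notes 12 and 13 to the schedule cap treatment at 12 months of post-remission (maintenance) therapy, and Section 5.2.13 lists unacceptable toxicity as a reason to come off. A responder can therefore stop while still in remission. Three things then follow:

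- **End of treatment (Section 7.8.2, Note 18).** A work-up that includes marrow and blood counts.
- **28 (+7) days after the last dose (Section 7.9, Note 19).** One clinic visit with blood counts, chemistry, and adverse event and concomitant medication review. For patients who stopped without confirmed progression, Section 7.9 adds: "please note the study may continue to request results of laboratory data conducted outside of the study". Note 19 has the same provision: "The study may continue to request results of laboratory data conducted outside of the study". Both run until progression is confirmed.
- **Afterwards (Section 7.10, Note 20).** "Each patient will be followed for survival every 3 months", "for a maximum of 2 years after the patient's final protocol-indicated treatment" at the longest. On method: "Survival contact can be made via clinic visit, chart review, obituary or similar observation". A death index or telephone call also counts.

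The 3-monthly contact lists no disease status, relapse date or subsequent therapy. The follow-up columns of Tables 2 and 3 show survival follow-up under Note 20 and nothing else beyond the 28-day visit.

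**The concern.** RFS needs a relapse date, or a date on which the patient was last known to be relapse-free. For a responder who stops in remission, the plan secures neither after about one month off treatment. A site that never sends an outside count or marrow report has still followed the protocol.

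An analysis rule can be written later. It cannot supply relapse or transplant dates that nobody was required to record. Without the date of a later transplant or donor cell infusion, neither RFS nor overall survival can be read apart from the effect of that treatment. Section 8.2.2 also plans to relate non-relapse deaths to immune data, and a late death can be classed that way only if relapse status before it is known.

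**Working it through.** The plan gives no RFS rate, event count or precision, so there is no stated figure to reproduce. The check has two parts.

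**1. What is required, by period**

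| Period after last dose | Disease status | Subsequent therapy |
|---|---|---|
| Up to 10 days (end of treatment) | Marrow and counts planned | Concomitant medications reviewed; procedures recorded (Section 5.2.11) |
| To 28 (+7) days | Counts | Concomitant medications and procedures recorded (Sections 7.1.4, 5.2.11) |
| Later, up to 2 years | Outside results, optional and unscheduled | Nothing specified |

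The gap begins after the 28-day visit.

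**2. What the gap could do to RFS**

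Number affected: at the 35% design response rate, 34 × 0.35 = 11.9, so about 12 responders.

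Every rate below is an assumption, not a document figure. Time runs from remission.

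- Median time to relapse 8 months: λr = ln 2 / 8 = 0.0866 per month.
- Non-relapse death: λd = 0.02 per month.
- A fraction f of 25-50% stops uniformly over months 0-6. The rest stop at 12 months. Stopping is independent of relapse risk.
- Median survival after relapse 2-6 months: λp = ln 2 / 2 = 0.3466 to ln 2 / 6 = 0.1155.

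*True 12-month RFS:* exp[−12 × (0.0866 + 0.02)] = exp(−1.280) = 0.278, or 28%.

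*Rule A: an unseen relapse counts only at death.* Patients who relapsed off treatment before month 12 and are alive at month 12 still look event-free. The excess is f × the average over stopping time u of ∫ from u to 12 of λr·exp[−(λr+λd)t]·exp[−λp(12−t)] dt. With δ = λp − λr − λd, this equals f × λr·exp(−12λp) × [exp(12δ) − average of exp(uδ)] / δ.

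- Low end (f = 0.25, 2 months): δ = 0.2399; 0.25 × 0.001354 × (17.80 − 2.24)/0.2399 = 0.022. Observed 0.278 + 0.022 = 0.300, or 30%.
- High end (f = 0.50, 6 months): δ = 0.00888; 0.50 × 0.02166 × (1.1125 − 1.0271)/0.00888 = 0.104. Observed 0.278 + 0.104 = 0.382, or 38%.
- If status is known until one month after stopping, which credits the 28-day visit, u becomes u + 1. The excess is then 0.021 to 0.093, and observed RFS is 30-37%.

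A simulation of 400,000 responders on the same inputs agrees.

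*Rule B: censor at the last disease assessment, taken as one month after stopping.* The simulated 12-month RFS is 28%, so there is no bias when stopping is unrelated to relapse risk. The last possible assessment is at 12 + 1 = 13 months, and nothing can be estimated after that. If patients who stop differ in relapse risk from those who continue, the bias can go either way. It is not quantified here.

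*Sensitivity.* A separate set of assumptions used median RFS of 4, 8 or 12 months, median time to stopping of 6 or 12 months capped at 12, and median survival after relapse of 3 or 6 months. Under Rule A, 12.5% became 17.5-25.7%, 35.4% became 40.7-48.5%, and 50.0% became 54.6-61.2%. That is about 5 to 13 points. Rule B was again unbiased at 12 months.

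**The case against.** The strongest reply is that the plan does provide for disease follow-up. There is an end-of-treatment marrow, a 28-day blood count, and a route to outside counts and marrow reports until progression is confirmed. Chart review is an allowed contact method, and Section 10.6.7 has sites keep source documents and linkable hospital records. RFS is descriptive, and by month 12 only 9-19% of responders relapse off treatment under the first set of assumptions: 11.9 × 0.09 = 1.1 to 11.9 × 0.19 = 2.3 patients. With 12 responders the standard error of a 28% estimate is √(0.28 × 0.72 / 12) = 0.13, or 13 points, which exceeds the largest shift of about 10. With enrollment planned to January 2024 and data lock in January 2025, late enrollees who complete 12 months of post-remission therapy have little or no off-treatment follow-up in any case.

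Much of that stands, and it rules out several stronger readings a reader might infer:

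- *Only vital status is collected once treatment stops, and relapses go uncollected.* Not supported. The end-of-treatment and 28-day assessments are planned, and later relapse collection is optional rather than absent.
- *RFS is bound to be overstated.* Not supported. That follows under Rule A but not under Rule B with non-informative stopping, and the plan states neither rule.
- *The adverse event cut-off in Note 3 and the timing rule in Section 7.8.2 depend on a date nobody collects.* Not supported. Both operate within 28 days of the last dose, when medications and procedures are recorded.
- *Late relapses could never be recovered.* Too strong. Retrieval from charts is possible, but no one is required to do it.

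The reply does not remove the gap itself. The request for outside results is discretionary, has no schedule, and does not cover later therapy. Sampling error is no reason to accept a shift that better collection would prevent.

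**Conclusion.** The point holds for the period after the 28-day visit. Relapse information for patients who stopped without relapse is then optional and unscheduled, later therapy is not collected, and vital status is the only required item, although RFS is a secondary objective.

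The direction and size of any effect depend on a rule the plan does not state. Under the assumed rates, 12-month RFS of 28% reads 30-38% if every off-treatment relapse is replaced by the death date, and 30-37% if status is known for one month after stopping. It stays at 28% with censoring and stopping unrelated to relapse risk, but cannot be estimated beyond about 13 months. Outside results that are in fact obtained shrink the overstatement towards zero.

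This concerns a secondary endpoint in about 12 patients. The primary composite CR rate and the overall survival death dates are unaffected. The change is worth making because it is cheap and because missing dates may be hard to recover later.

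**What to change.** 1. In Section 7.10, Note 20 and the follow-up columns of Tables 2 and 3, require three items at each existing 3-monthly contact for patients who stopped without relapse: (a) relapse status and date, from local counts or marrow reports; (b) date and type of the first subsequent anti-leukemia or cellular therapy, including donor cell infusion or second transplant; (c) date last known relapse-free.
2. In Note 19 and Section 7.9, change the permissive *may* to *will request*.
3. In Section 9.3.1, name RFS and state its time origin, events and censoring, including how subsequent therapy is handled. If progression-free survival is also intended, define it separately.

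The cost is three additional eCRF items and some site data entry at contacts already planned, using chart review that is already allowed. Vital status alone would no longer suffice for a living patient in remission. No visit or marrow is added, and treatment is unchanged.
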